8.1. Efficacy Assessments

Not applicable.

8.2. Safety Assessments

Planned time points for all safety assessments are provided in the [SoA](#). Unscheduled clinical laboratory measurements may be obtained at any time during the study to assess any perceived safety issues.

8.2.1. Physical Examinations

A complete physical examination will include, at a minimum, head, ears, eyes, nose, mouth, skin, heart and lung examinations, lymph nodes, and gastrointestinal, musculoskeletal, and neurological systems.

A brief physical examination will include, at a minimum, assessments of general appearance, the respiratory and cardiovascular systems, and participant-reported symptoms.

Physical examinations may be conducted by a physician, trained physician's assistant, or nurse practitioner as acceptable according to local regulation.

Physical examination findings collected during the study will be considered source data and will not be required to be reported, unless otherwise noted. Any untoward physical examination findings that are identified during the active collection period and meet the definition of an AE or SAE ([Appendix 3](#)) must be reported according to the processes in [Sections 8.3.1 to 8.3.3](#).

8.2.2. Vital Signs

Supine BP will be measured with the participant's arm supported at the level of the heart, and recorded to the nearest mm Hg after approximately 5 minutes of rest. The same arm (preferably the dominant arm) will be used throughout the study. Participants should be instructed not to speak during measurements.

The same properly sized and calibrated BP cuff will be used to measure BP each time. The use of an automated device for measuring BP and pulse rate is acceptable; however, when done manually, pulse rate will be measured in the brachial/radial artery for at least 30 seconds. When the timing of these measurements coincides with a blood collection, BP and pulse rate should be obtained prior to the nominal time of the blood collection.

Additional collection times, or changes to collection times, of BP and pulse rate will be permitted, as necessary, to ensure appropriate collection of safety data.

8.2.3. Electrocardiograms

Standard 12-lead ECGs utilizing limb leads (with a 10 second rhythm strip) should be collected at times specified in the [SoA](#) section of this protocol using an ECG machine that automatically calculates the heart rate and measures PR, QT, and QTc intervals and QRS complex. Alternative lead placement methodology using torso leads (eg, Mason-Likar) should not be used given the potential risk of discrepancies with ECGs acquired using standard limb lead placement. All scheduled ECGs should be performed after the participant has rested quietly for at least 5 minutes in a supine position.

To ensure safety of the participants, a qualified individual at the investigator site will make comparisons to baseline measurements. Additional ECG monitoring will occur if a) a postdose QTcF interval is increased by ≥ 60 msec from the baseline **and** is > 450 msec; or b) an absolute QT value is ≥ 500 msec for any scheduled ECG. If either of these conditions occurs, then 2 additional ECGs will be collected approximately 2 to 4 minutes apart to confirm the original measurement. If the QTc values from these repeated ECGs remain above the threshold value, then a single ECG must be repeated at least hourly until QTc values from 2 successive ECGs fall below the threshold value that triggered the repeat measurement.

If a) a postdose QTcF interval remains ≥ 60 msec from the baseline **and** is > 450 msec; or b) an absolute QT value is ≥ 500 msec for any scheduled ECG for greater than 4 hours (or sooner, at the discretion of the investigator); or c) QTcF intervals get progressively longer, the participant should undergo continuous ECG monitoring. A cardiologist should be consulted if QTcF intervals do not return to less than the criteria listed above after 8 hours of monitoring (or sooner, at the discretion of the investigator).

In some cases, it may be appropriate to repeat abnormal ECGs to rule out improper lead placement as contributing to the ECG abnormality. It is important that leads be placed in the same positions each time in order to achieve precise ECG recordings. If a machine-read QTc value is prolonged, as defined above, repeat measurements may not be necessary if a qualified medical provider's interpretation determines that the QTcF values are in the acceptable range.

ECG values of potential clinical concern are listed in [Appendix 7](#).

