15. Use of prescription or nonprescription drugs and dietary and herbal supplements within 7 days or 5 half-lives (whichever is longer) prior to the first dose of study intervention. (Refer to [Section 6.8](#) Concomitant Therapy for additional details).

Prior/Concurrent Clinical Study Experience:

16. Previous administration with an investigational drug within 30 days (or as determined by the local requirement) or 5 half-lives preceding the first dose of study intervention used in this study (whichever is longer).

Diagnostic Assessments:

17. A positive urine drug test.
18. Screening supine BP ≥ 140 mm Hg (systolic) or ≥ 90 mm Hg (diastolic), following at least 5 minutes of supine rest. If BP is ≥ 140 mm Hg (systolic) or ≥ 90 mm Hg (diastolic), the BP should be repeated 2 more times and the average of the 3 BP values should be used to determine the participant's eligibility.
19. Baseline standard 12-lead ECG that demonstrates clinically relevant abnormalities that may affect participant safety or interpretation of study results (eg, baseline QTcF interval >450 msec, complete LBBB, signs of an acute or indeterminate-age myocardial infarction, ST-T interval changes suggestive of myocardial ischemia, second- or third-degree AV block, or serious bradyarrhythmias or tachyarrhythmias). If the baseline uncorrected QT interval is >450 msec, this interval should be rate-corrected using the Fridericia method and the resulting QTcF should be used for decision making and reporting. If QTcF exceeds 450 msec, or QRS exceeds 120 msec, the ECG should be repeated 2 more times and the average of the 3 QTcF or QRS values should be used to determine the participant's eligibility. Computer-interpreted ECGs should be overread by a physician experienced in reading ECGs before excluding a participant.
20. Participants with ANY of the following abnormalities in clinical laboratory tests at screening, as assessed by the study-specific laboratory and confirmed by a single repeat test, if deemed necessary:
 - AST or ALT level $\geq 1.5 \times$ ULN;

- Total bilirubin level $\geq 1.5 \times$ ULN; participants with a history of Gilbert's syndrome may have direct bilirubin measured and would be eligible for this study provided the direct bilirubin level is \leq ULN.
- eGFR ≤ 90 mL/min/1.73m² based on CKD-EPI equation.

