7.1.2. ECG Changes

A participant who meets either bulleted criteria based on the average of triplicate ECG readings will be withdrawn from the study interventions.

- QTcF >500 msec.

- Change from baseline: QTcF >60 msec and QTcF >450 msec.

If a clinically significant finding is identified (including, but not limited to, changes from baseline in QTcF after enrollment), the investigator or qualified designee will determine if the participant can continue in the study and if any change in participant management is needed. This review of the ECG printed at the time of collection must be documented. Any new clinically relevant finding should be reported as an AE.

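### The 500 msec repeat-ECG trigger in Protocol 8.2.3 is written on QT, while the withdrawal limit in 7.1.2 is on QTcF, so a narrow set of readings above the limit has no mandated confirmation

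*Protocol*

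**What the plan says.** Protocol 8.2.3 (Electrocardiograms) gives two conditions, either of which requires two further ECGs a few minutes apart:

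- (a) QTcF has risen by at least 60 msec from baseline and is above 450 msec.
- (b) "an absolute QT value is ≥ 500 msec for any scheduled ECG".

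The continuous-monitoring rule in the next paragraph uses the same two conditions, with persistence beyond 4 hours. It adds (c), QTcF becoming progressively longer.

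The rest of 8.2.3 works on corrected values. Hourly repeats follow "If the QTc values from these repeated ECGs remain above the threshold value". Escalation reads "A cardiologist should be consulted if QTcF intervals do not return to less than the criteria listed above". Repeats may be skipped if a qualified reader's "interpretation determines that the QTcF values are in the acceptable range". The section also lists QT and QTc as separate machine measurements.

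Protocol 7.1.2 (ECG Changes) states: "A participant who meets either bulleted criteria based on the average of triplicate ECG readings will be withdrawn from the study interventions". The first criterion is "QTcF >500 msec". The second is a QTcF rise above 60 msec with QTcF above 450 msec.

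The Schedule of Activities (1.3) specifies single ECGs. Exclusion 19 (5.2) gives "baseline QTcF interval >450 msec" as an example of an excluding abnormality and orders two repeats when that value is exceeded, but only to decide eligibility. Appendix 7 lists QTcF above 500 msec as a finding that may qualify as an SAE. SAP 6.2.4 lists any single post-dose QTcF of 500 msec or more.

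**The concern.** The withdrawal limit can be applied only to a triplicate average, and after dosing 8.2.3 is the only text that orders the extra two readings. Its trigger should therefore fire whenever a single scheduled reading is above the QTcF limit. Condition (a) does most of this. Condition (b) should cover the remainder, but it uses a different quantity. At heart rates above 60 bpm QT is shorter than QTcF, so a QTcF above 500 msec can occur with QT below 500 msec.

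The same word upsets the stopping rule. Repeats are judged by comparing QTc with the threshold that triggered them, but under (b) that threshold is a QT value. This affects every trigger under (b), not only the narrow window.

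A participant could thus have a single QTcF above 500 msec with no required confirmation, and the average on which withdrawal depends might never be obtained. As the schedule table reads, the second on-treatment ECG is on Period 2 Day 12, the day of discharge. Section 4.1 makes discharge conditional on review of safety laboratory results. Routine follow-up is a telephone contact 28 to 35 days after the last dose. A Day 12 reading in this window would carry no mandated repeat before discharge.

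**Working it through.** The documents give no figure on this point to reproduce. The check asks which readings have QTcF above 500 msec and meet neither (a) nor (b).

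**Inputs**
- Fridericia correction (SAP 3.5.4): QTcF = QT / RR^(1/3), with RR = 60/HR.
- Conditions (a) and (b): Protocol 8.2.3.
- Withdrawal limit: Protocol 7.1.2.
- Baseline QTcF at most 450 msec, taken from exclusion 19.

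**Step 1: what (a) misses.** A QTcF above 500 escapes (a) only if the rise is below 60, so baseline must exceed QTcF − 60. In whole msec, QTcF 501 needs a baseline of at least 442, and a baseline of 450 allows QTcF up to 509.

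| Baseline QTcF | Post-dose QTcF missed by (a) |
|---|---|
| 441 or less | none |
| 442 | 501 |
| 445 | 501–504 |
| 448 | 501–507 |
| 450 | 501–509 |

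This gives 1 + 2 + … + 9 = 45 whole-msec pairs. That is a count of cells, not a probability. The second withdrawal criterion is always covered, because a rise above 60 with QTcF above 450 satisfies (a).

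**Step 2: what (b) misses.** QT = QTcF × (60/HR)^(1/3) is below 500 when HR > 60 × (QTcF/500)³:

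- QTcF 501: 60 × 1.002³ = 60.4 bpm
- QTcF 505: 60 × 1.010³ = 61.8 bpm
- QTcF 509: 60 × 1.018³ = 63.3 bpm

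**Step 3: both together.** The uncovered set is baseline 442–450, QTcF 501–509, rise below 60 and heart rate above about 60 to 63 bpm. Example: baseline 448 and QTcF 505 at 75 bpm. The rise is 505 − 448 = 57, and QT = 505 × 0.8^(1/3) = 468.8. Neither condition fires.

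A grid over baseline 360–450, heart rate 40–120 and QT 300–599, in unit steps, agrees. The uncovered points have QTcF from 500.01 to 509.95, a lowest heart rate of 61 and a lowest baseline of 441 (for fractional QTcF between 500 and 501).

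**Step 4: behaviour of (b) elsewhere.** QTcF when QT is exactly 500:

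| HR (bpm) | 45 | 50 | 55 | 58 | 60 | 65 | 70 | 75 | 80 |
|---|---|---|---|---|---|---|---|---|---|
| QTcF (msec) | 454.3 | 470.5 | 485.7 | 494.4 | 500.0 | 513.5 | 526.4 | 538.6 | 550.3 |

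Above 60 × 1.02³ = 63.7 bpm, (b) fires only at QTcF above 510, where (a) already fires for every baseline up to 450, so (b) adds nothing. Below 60 bpm, (b) is more sensitive than a QTcF trigger.

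**Step 5: after correction.** With (b) read as QTcF ≥500, the grid has no uncovered point. Adding QT as an alternative can only widen the trigger, so the set stays empty.

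**Step 6: exposure.** As the schedule reads, on-treatment ECGs fall on Period 2 Days 11 and 12: about 10 participants × 2 = 20 readings. Dosing ends on Day 11.

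**The case against.** The strongest reply is that 8.2.3 should be read as a whole. The printed adjective is *absolute*, which elsewhere in the protocol (Table 3, Appendix 7) contrasts a corrected value with its change from baseline. Exclusion 19 says *uncorrected* when it means that. The repeat rule, the over-read exception and the cardiology rule all use corrected values. On that reading (b) already means QTc and nothing is uncovered. This is probably what was intended. But 8.2.3 names QT and QTc separately and prints QT in both rules, so a site following the words would apply QT. The surrounding corrected-value wording shows the intent and also shows that the printed trigger conflicts with it.

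Second, 7.1.2 cannot be applied without a triplicate, so repeats are implied, and one reading is not itself a breach of a limit defined on an average. That is fair, but an implication is weaker than the explicit instruction given for every other trigger.

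Third, other safeguards exist. Under 7.1.2, for a clinically significant finding, "the investigator or qualified designee will determine if the participant can continue in the study", with documented review. Section 8.2.3 allows optional repeats, and condition (c) can start continuous monitoring. Section 8 requires safety issues to be discussed with the sponsor, and Appendix 7 recommends alerts. A competent site would very likely repeat the ECG. None of these texts orders the two confirmatory readings.

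Fourth, the count of 20 readings depends on a schedule table whose columns may be shifted in the available text, since the discharge mark does not sit under Day 12. If the ECG marks are also one column out, the only scheduled on-treatment ECG follows the last dose and no dose could be averted. This stands, and it lowers the priority.

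**Conclusion.** The concern holds on the literal text, as a low-priority wording correction to an operative safety rule. The uncovered window is QTcF 501–509 msec with baseline 442–450 msec and heart rate above about 60 to 63 bpm. The documents give no QTcF distribution, so no probability can be attached to it. At most one dose could be averted, and possibly none, because the Day 11 ECG is not timed relative to the dose.

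The result assumes Fridericia correction, the printed word QT, and a baseline within the eligibility limit of 450 msec. If the Period 1 Day 1 pre-dose baseline (SAP 3.4) were higher, the window would widen: at 460 msec it would run from 500 to 520. The PK analysis and the SAP outputs do not depend on it.

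**What to change.** In both places in 8.2.3, make condition (b) refer to *QT or QTcF* of at least 500 msec, and state that repeats under (b) are judged on QTcF ≥500 msec. Any single QTcF above the 7.1.2 limit then triggers the two confirmatory ECGs, subject to the existing over-read exception, and the stopping rule compares like with like.

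Replacing QT by QTcF outright would also close the window. It would, however, drop the trigger below 60 bpm when QT is at least 500 but QTcF is lower (471 at 50 bpm), unless (a) fires. Keeping both avoids that loss.

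The cost is a few words in two sentences, one clarifying phrase, and two extra ECGs per newly triggered reading among about 20. Section 7.1.2, Appendix 7 and the SAP need no change.

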8.2.4. Clinical Safety Laboratory Assessments

See [Appendix 2](#) for the list of clinical safety laboratory tests to be performed and the [SoA](#) for the timing and frequency. All protocol-required laboratory assessments, as defined in [Appendix 2](#), must be conducted in accordance with the laboratory manual and the [SoA](#). Unscheduled clinical laboratory measurements may be obtained at any time during the study to assess any perceived safety issues.

The investigator must review the laboratory report, document this review, and record any clinically relevant changes occurring during the study in the AE section of the CRF. Clinically significant abnormal laboratory findings are those which are not associated with the underlying disease, unless judged by the investigator to be more severe than expected for the participant's condition.

All laboratory tests with values considered clinically significantly abnormal during participation in the study or within 28 calendar days after the last dose of study intervention should be repeated until the values return to normal or baseline or are no longer considered clinically significant by the investigator or medical monitor.

If such values do not return to normal/baseline within a period of time judged reasonable by the investigator, the etiology should be identified and the sponsor notified.

See [Appendix 6](#) for suggested actions and follow-up assessments in the event of potential drug-induced liver injury.

Participants may undergo random urine drug testing at the discretion of the investigator. Drug testing conducted prior to dosing must be negative for participants to receive study intervention.

8.2.5. COVID-19 Specific Assessments

Participants will be tested for SARS-COVID-19 infection by PCR prior to being admitted to the clinic for confinement and if they develop COVID-19 like symptoms. Additional testing may be required by local regulations or by the PI.

8.2.6. Pregnancy Testing

Pregnancy tests may be urine or serum tests, but must have a sensitivity of at least 25 mIU/mL. Pregnancy tests will be performed in WOCBP at the times listed in the [SoA](#). Following a negative pregnancy test result at screening, appropriate contraception must be commenced and a second negative pregnancy test result will be required at the baseline visit prior the participant's receiving the study intervention. Pregnancy tests will also be done whenever 1 menstrual cycle is missed during the active treatment period (or when potential pregnancy is otherwise suspected) and at the end of the study. Pregnancy tests may also be repeated if requested by IRBs/ECs or if required by local regulations. If a urine test cannot be confirmed as negative (eg, an ambiguous result), a serum pregnancy test is required. In such cases, the participant must be excluded if the serum pregnancy result is positive.

8.3. Adverse Events, Serious Adverse Events, and Other Safety Reporting

The definitions of an AE and an SAE can be found in [Appendix 3](#).

AEs may arise from symptoms or other complaints reported to the investigator by the participant (or, when appropriate, by a caregiver, or surrogate), or they may arise from clinical findings of the Investigator or other healthcare providers (clinical signs, test results, etc.).

The investigator and any qualified designees are responsible for detecting, documenting, and recording events that meet the definition of an AE or SAE and remain responsible to pursue and obtain adequate information both to determine the outcome and to assess whether the event meets the criteria for classification as an SAE or caused the participant to discontinue the study (see [Section 7.1](#)).

During the active collection period as described in [Section 8.3.1](#), each participant/legal guardian/legally authorized representative will be questioned about the occurrence of AEs in a nonleading manner.

In addition, the investigator may be requested by Pfizer Safety to obtain specific follow-up information in an expedited fashion.

8.3.1. Time Period and Frequency for Collecting AE and SAE Information

The time period for actively eliciting and collecting AEs and SAEs (“active collection period”) for each participant begins from the time the participant provides informed consent, which is obtained before the participant’s participation in the study (eg, before undergoing any study-related procedure and/or receiving study intervention), through and including a minimum of 28 calendar days, after the last administration of the study intervention.

Follow-up by the investigator continues throughout and after the active collection period and until the AE or SAE or its sequelae resolve or stabilize at a level acceptable to the investigator.

For participants who are screen failures, the active collection period ends when screen failure status is determined.

If the participant withdraws from the study and also withdraws consent for the collection of future information, the active collection period ends when consent is withdrawn.

If a participant permanently discontinues or temporarily discontinues study intervention because of an AE or SAE, the AE or SAE must be recorded on the CRF and the SAE reported using the CT SAE Report Form.

Investigators are not obligated to actively seek information on AEs or SAEs after the participant has concluded study participation. However, if the investigator learns of any SAE, including a death, at any time after a participant has completed the study, and he/she

considers the event to be reasonably related to the study intervention, the investigator must promptly report the SAE to Pfizer using the CT SAE Report Form.

8.3.1.1. Reporting SAEs to Pfizer Safety

All SAEs occurring in a participant during the active collection period as described in [Section 8.3.1](#) are reported to Pfizer Safety on the CT SAE Report Form immediately upon awareness and under no circumstance should this exceed 24 hours, as indicated in [Appendix 3](#). The investigator will submit any updated SAE data to the sponsor within 24 hours of it being available.

8.3.1.2. Recording Nonserious AEs and SAEs on the CRF

All nonserious AEs and SAEs occurring in a participant during the active collection period, which begins after obtaining informed consent as described in [Section 8.3.1](#), will be recorded on the AE section of the CRF.

The investigator is to record on the CRF all directly observed and all spontaneously reported AEs and SAEs reported by the participant.

Reporting of AEs and SAEs for participants who fail screening are subject to the CRF requirements as described in [Section 5.4](#).

8.3.2. Method of Detecting AEs and SAEs

The method of recording, evaluating, and assessing causality of AEs and SAEs and the procedures for completing and transmitting SAE reports are provided in [Appendix 3](#).

Care will be taken not to introduce bias when detecting AEs and/or SAEs. Open-ended and nonleading verbal questioning of the participant is the preferred method to inquire about AE occurrences.

8.3.3. Follow-Up of AEs and SAEs

After the initial AE or SAE report, the investigator is required to proactively follow each participant at subsequent visits/contacts. For each event, the investigator must pursue and obtain adequate information until resolution, stabilization, the event is otherwise explained, or the participant is lost to follow-up (as defined in [Section 7.3](#)).

In general, follow-up information will include a description of the event in sufficient detail to allow for a complete medical assessment of the case and independent determination of possible causality. Any information relevant to the event, such as concomitant medications and illnesses, must be provided. In the case of a participant death, a summary of available autopsy findings must be submitted as soon as possible to Pfizer Safety.

Further information on follow-up procedures is given in [Appendix 3](#).

